15.4. Unreportable adverse events

The following adverse events do not need to be reported if occurred in the timeframe indicated below.

Table 5. Unreportable adverse events

Unreportable adverse event	Time frame	Rationale
Haemoptysis	<48h	May occur after bronchoscopy by causing damage to the airway walls or taking biopsies in the lung parenchyma. These inconveniences will disappear within 48 hours.
Fever	<48h	May occur after the procedure. Is no reason for alarm and can be treated with antipyretic medication, such as paracetamol.

16. Vulnerable population

This section is not applicable. No vulnerable population.

17. (Early) termination or suspension of the feasibility clinical investigation

There are no provisions or interim analyses planned that can result in early termination of the trial. The principal investigator, MEC, or regulatory authority may suspend or prematurely terminate participation in the clinical investigation at the investigation sites for which they are responsible.

Any signs of unknown or increased risks for the subjects will be discussed by the sponsor and investigator to assess the impact on the subjects and clinical investigation. If suspicion of an unacceptable risk to subjects arises during the clinical investigation, or when so instructed by the MEC or regulatory authorities, the sponsor shall suspend the clinical investigation while the risk is assessed.

The sponsor shall terminate the clinical investigation if an unacceptable risk is confirmed.

If suspension or premature termination occurs, the terminating party shall justify its decision in writing and promptly inform the other parties with whom they are in direct communication. The principal investigator and sponsor shall keep each other informed of any communication received from either the MEC or the regulatory authority.

Serious or repetitive occurrences of deviations from study protocol or non-compliance with regulations may also be the reason for early termination or suspension of a study site. In such situations, there is no change to the planned standard of care follow-up of patients, and follow-up of adverse events.

IGT Systems	Feasibility Clinical Investigation Protocol AirWaze – easy and advanced tools for CBCT guided lung interventions	Doc ID: XCY607-130895 Rev: 04 Date: 2024-Jun-19 Page 39 of 56
-------------	--	--

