- The cognitive load of pulmonologists during the navigation towards the first lesion will be measured with the Surgical Task Load Index (SURG-TLX) which is a validated method for measuring cognitive load. The questionnaire is asked after tool-in-lesion confirmation (either rEBUS, CBCT, or CBCT-FS) ^{12,16,17} (Appendix V).
- Radiation exposure for patients will be measured in effective dose (mSv) and DAP (Gy·cm²) per procedure including fluoroscopy, CBCT and CBCT-FS radiation dose. The fluoroscopy time (minutes) will be measured as well (Appendix V).
- Radiation exposure for the staff is measured in an average scattered effective dose (mSv) per procedure at hand and chest (Appendix V).
- Report all adverse events (including but not limited to pneumonia, pneumothorax, bleeding/hemorrhage).
- Report all adverse device effects.
- Report all device deficiencies. Device deficiencies that could have led to an SAE need to be reported in the Clinical Study End Report.

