8.7.7. Secondary objective: Adverse events

Objective

Report all adverse events, except for the unreportable adverse events (section 15.4).

Endpoint

Adverse events, including information on the seriousness, treatment needed, resolution and relevant judgment concerning the causal relationship with the investigational devices, comparator or procedure will be summarized for safety information.

Analysis

The objective is descriptive with no performance requirements and no sample size has been calculated. All subjects will be included in this analysis.

IGT Systems	Feasibility Clinical Investigation Protocol AirWaze – easy and advanced tools for CBCT guided lung interventions	Doc ID: XCY607-130895 Rev: 04 Date: 2024-Jun-19 Page 30 of 56
-------------	--	--

All adverse events will be presented in a tabular format.

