8.7.8. Secondary objective: Adverse Device Effects

Objective

Report all adverse device effects.

Endpoint

Adverse device effects, including information on the seriousness, treatment needed, resolution and relevant judgment concerning the causal relationship with the investigational devices or procedure will be summarized for safety information.

Analysis

The objective is descriptive with no performance requirements and no sample size has been calculated. All subjects will be included in this analysis.

All adverse device effects will be presented in a tabular format.

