Device Deficiencies Note: Any Investigational Device Deficiency that might have led to a serious adverse event if a) suitable action had not been taken or b) intervention had not been made or c) if circumstances had been less fortunate is considered a reportable event.	Complete eCRF page with all available new and updated information	• Within 3 calendar days of first becoming aware of the event • Reporting required through the end of the study

The investigator shall supply the Sponsor, upon the Sponsor's request, with any additional information related to the safety reporting of a particular event. The Sponsor and Monitor can request access to this information at any time.

Any adverse event experienced by the subject from the time of signing the informed consent until the 1-week follow-up visit will be recorded on the e-CRF. All AEs that are considered related to the investigational device or procedure will be followed until they have abated, or until a stable situation has been reached.

The e-CRF will include the following information for adverse events: date of the adverse event, description, actions taken (including treatment), resolution, assessment of both the seriousness and the relationship to the investigational device, comparator and procedure. Information collected for device deficiencies is the date of device deficiency, whether this could have led to a Serious Adverse Device Effect (SADE) if a) suitable action had not been taken or b) intervention had not been made or c) if circumstances had been less fortunate.

Sponsor will ensure review of the investigator's assessment of all adverse events and device deficiencies. Ongoing safety evaluation of the investigational device will be done to determine whether risk analysis needs to be updated.

The Sponsor shall report to the competent authority and/or MEC all reportable events and safety updates as required following the reporting requirements and within the specified timelines as required per local legislation.

Where necessary to ensure timely reporting, the sponsor may submit an initial report that is incomplete followed by a complete report.

IGT Systems	Feasibility Clinical Investigation Protocol AirWaze – easy and advanced tools for CBCT guided lung interventions	Doc ID: XCY607-130895 Rev: 04 Date: 2024-Jun-19 Page 36 of 56
-------------	--	--

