15.3. Anticipated adverse device effects

Anticipated adverse device effects are described below in *Table 4*.

Table 4. Anticipated adverse device effects.

Anticipated adverse device effects		Severity	Likely incidence (PoH)	Risk category	Mitigation or treatment
Hazardous situation	Possible harm				
Wrong treatment decisions due to errors or missing information in Investigational Device.	Patient exposed to inadequate / inappropriate treatment or diagnostic exposure during clinical use (F10)	S1	PoH 2 - Not expected to occur (10— <100 per 1000000)	Acceptable	Add a message in the user manual stating that feature is not for clinical decision-making.
Permanent malfunction of the Interventional Tool or Interventional Workstation during an interventional procedure due to software or hardware failure. The result is that the user needs to continue the procedure on X-Ray modality without the Interventional Tool.	No Health Consequences or Impact (F26)	S0	PoH 2 - Not expected to occur (10— <100 per 1000000)	Acceptable	No measures need to be taken
The C-arc has been moved in the longitudinal and/or transversal direction invalidating the current registration.	Patient exposed to incorrectly deployed biopsy/ablation tools during clinical use Possible harm is: - Bronchial hemorrhage (E0707) - Pneumothorax (E0734) - Procedure related complications (E21) - Delay to treatment/therapy (F05)	S2	PoH 2 - Not expected to occur (10— <100 per 1000000)	Acceptable	In the IFU, inform the clinical user that the C-arc should not be moved in the longitudinal and/or transversal direction anymore after planning, and what the possible impact is when it happens.
The planned path is not at the right location due to a badly geometrically calibrated system (deviation after a long use), so the geometry space of 3D image is not matching the geometry space of 2D images (fluoro).	Patient exposed to incorrectly deployed biopsy/ablation tools during clinical use Possible harm is: - Bronchial hemorrhage (E0707) - Pneumothorax (E0734) - Procedure related complications (E21) - Delay to treatment/therapy (F05)	S2	PoH 2 - Not expected to occur (10— <100 per 1000000)	Acceptable	Standard (field) service procedures will detect and correct badly calibrated systems.

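### Section 15.4 makes haemoptysis and fever within 48 hours unreportable with no limit on seriousness or device relation, which contradicts the unqualified AE, SAE and ADE rules elsewhere and can hide early bleeding

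*Combined protocol and SAP*

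**What the plan says.** Section 15.4 opens with "The following adverse events do not need to be reported if occurred in the timeframe indicated below". Table 5 then lists two events, haemoptysis and fever, each with a time frame of <48h and a rationale. For haemoptysis the rationale ends "These inconveniences will disappear within 48 hours"; for fever it reads "Is no reason for alarm and can be treated with antipyretic medication, such as paracetamol". There is no criterion for severity, seriousness, treatment or device relation.

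Section 8.7.7 takes the exemption into the analysis: "Report all adverse events, except for the unreportable adverse events (section 15.4".

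Other sections have no such exception:
- Section 7.1.1, secondary endpoints: "Report all adverse events (including but not limited to pneumonia, pneumothorax, bleeding/hemorrhage").
- Section 7.4, Follow-up: all AEs up to the 1-week visit are collected, and hospital stays prolonged by procedural complications are named.
- Section 15.2: the investigator reports any AE through the e-CRF form, and SAEs within 3 calendar days. Any AE from consent "until the 1-week follow-up visit will be recorded on the e-CRF".
- Section 8.7.8: "Report all adverse device effects".

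Table 4 in section 15.3 names "Bronchial hemorrhage (E0707") as a possible harm of overlay and registration errors.

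**The concern.** The rationale column describes a mild, passing event, but the rule is written by event name and time alone. Read literally, it also covers an early haemoptysis or fever that meets the SAE definition in section 15.1, or one that follows a wrong overlay. Nothing says which rule prevails when section 15.4 meets section 15.2.

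Safety reporting is a stated secondary objective, and section 8.2 says the study will inform a pivotal design. Section 15.2 makes the e-CRF entry the place where seriousness and relation to device and procedure are assessed, and the sponsor reviews that assessment and feeds it into the risk analysis. A site that follows section 15.4 and makes no entry leaves nothing to review. Section 17 plans no interim analysis, so any response to increased risk depends on such signs being seen. An event that was never entered may not be recoverable after database lock.

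**Working it through.** This is mainly a check of text against text.

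**1. Is the exemption limited?** No. Only a name and <48h define it. The milder words stand in the rationale and do not restrict the rule. The window is also unclear: the opening sentence of 15.4 points to time of onset, while the haemoptysis rationale points to duration.

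**2. Test case.** Take haemoptysis 12 hours after biopsy that prolongs the admission.
- Section 15.1: prolonged hospitalization makes it an SAE.
- Section 15.2: report within 3 calendar days and record on the e-CRF.
- Section 7.4: collect.
- Section 15.4: need not be reported.
- Section 8.7.7: outside the AE objective.

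The two sets of rules cannot both be followed. Reading 15.4 as recorded but not reported does not help, because 15.2 makes the e-CRF form the reporting route.

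**3. Overlap with the named device harm.** Table 4 has six hazards rated S2, meaning that professional medical intervention is needed. Five list bronchial hemorrhage first; the sixth lists rupture of an airway or vessel. Table 5 itself attributes haemoptysis to airway-wall damage or biopsy. No section says how haemoptysis is told apart from bronchial hemorrhage.

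**4. Does section 8.7.8 close the gap?** Not by itself. Section 15.1 defines an ADE as an AE related to use of the device, and relation is assessed on the AE entry. Without an entry there is no causality judgement, so the event cannot be identified as an ADE.

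**5. Size.** Inputs: 37 subjects and 33 per protocol with 10% dropout (section 8.2); 10 to <100 harms per 1,000,000 examinations for each hazard (Tables 3 and 4).
- The plan's own figure: 33 / (1 − 0.10) = 36.7, rounded up to 37, as stated. The point does not depend on it.
- All early haemoptysis. The documents give no rate, so a range p is assumed. Expected events = 37p; chance of at least one = 1 − (1 − p)^37.

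| Assumed p | Expected events | Chance of at least one |
|---|---|---|
| 1% | 0.37 | 31% |
| 3% | 1.11 | 68% |
| 5% | 1.85 | 85% |
| 10% | 3.7 | 98% |

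- Device-caused harm at the risk file's incidence, counting one procedure as one examination. At 10 per million: 1 − (1 − 0.00001)^37 = 0.037%. At 100 per million: 1 − (1 − 0.0001)^37 = 0.37%. Over the five hazards that list bronchial hemorrhage, expected events are below 5 × 37 × 0.0001 = 0.0185.

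**The case against.** A reader might infer that section 15.4 removes the bleeding harm from the safety analysis. The documents do not support that. The exempt term is haemoptysis and the risk-file harm is bronchial hemorrhage; the two are not equated. Bleeding seen at bronchoscopy and recorded as hemorrhage stays reportable, as does haemoptysis after 48 hours. Section 7.1.1 names bleeding, section 8.7.8 has no exception, and the end-procedural form (Appendix V, Part C) asks about AEs and ADEs. All of this stands, and it confines the point to bleeding that presents as early haemoptysis.

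For non-serious events, section 8.7.7 cites 15.4 expressly, so the exemption reads as deliberate, and the wording of Table 5 suggests that mild events were meant. That also stands: the conflict that matters concerns serious or device-related events.

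A reader might also infer that a serious early bleed could lawfully go unreported. The documents do not show this. Section 15.2 has an unqualified SAE duty and refers sponsor reporting to local legislation, and section 13 commits to ISO 14155 and the Medical Device Regulation. The contradiction is within the protocol.

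Finally, a reader might put an upper confidence limit on a zero count (0 of 37 gives an exact two-sided limit of 1 − 0.025^(1/37) = 9.5%) and call it invalid. The arithmetic is right, but section 8.7.7 plans descriptive tables and no such limit.

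**Conclusion.** The concern holds in a limited form. Section 15.4 exempts haemoptysis and fever within 48 hours whatever their seriousness or device relation, and section 8.7.7 carries this into the AE analysis. That contradicts sections 7.1.1, 7.4 and 15.2 and undercuts the ADE objective in 8.7.8. The consequence is that serious or device-related cases presenting as early haemoptysis or fever can go without assessment and be missing from the safety tables.

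The number affected is unknown. It is 0.4 to 3.7 early haemoptyses in 37 subjects if the true rate is 1% to 10%, which is an assumption, and most of these could be mild. A device-caused bleed at the risk file's own incidence would very probably not occur at all in 37 procedures. The conclusion therefore rests on the contradiction, which is present at any rate. The primary endpoints are not affected.

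**What to change.** In section 15.4, state that the exemption covers only events that are non-serious under section 15.1 and not suspected to be device-related, and that all SAEs and ADEs stay reportable under sections 15.2 and 8.7.8. State whether <48h means onset or duration. State how haemoptysis is distinguished from bronchial hemorrhage. Then align sections 7.1.1, 7.4, 8.7.7 and 15.2 with that text. A limit framed as no treatment beyond that named in Table 5 would not work for haemoptysis, because Table 5 names none.

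Optionally, add one yes/no e-CRF field so that exempted events are counted in the safety table.

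Cost: one paragraph, matching edits, and a protocol amendment that may need ethics committee submission under section 10. There would be a few more AE entries and a brief judgement on device relation for mild events. Enrolment began in October 2023, so subjects already enrolled would lack the optional field, and the report should say so. The change concerns reporting only, not patient care.

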Appendix I: System Usability Scale (SUS) of AirWaze

The System Usability Scale (SUS) is a reliable tool for measuring the overall usability of a product or service. This score represents how usable and learnable the product or service is. The SUS questionnaire for the AirWaze investigational device will be conducted after every 4 procedures per operator. In total, the SUS questionnaire will be conducted approximately 9 times. The questionnaire consists of a 10-item questionnaire with five response options for respondents; from Strongly agree to Strongly disagree ¹⁵.

Please indicate how much you disagree or agree with the following statements:	Strongly Disagree	Disagree	Neutral	Agree	Strongly Agree
1. I think that I would like to use the AirWaze Software Device frequently.					
2. I found the AirWaze Software Device unnecessarily complex.					
3. I thought the AirWaze Software Device is easy to use.					
4. I think that I would need the support of a technical person to be able to use the AirWaze Software Device.					
5. I found the various functions in the AirWaze Software Device were well integrated.					
6. I thought there was too much inconsistency in the AirWaze Software Device.					
7. I imagine that most people would learn to use these AirWaze Software Device very quickly.					
8. I found the AirWaze Software Device very awkward to use.					
9. I felt very confident using the AirWaze Software Device system.					
10. I needed to learn a lot of things before I could get going with these AirWaze Software Device.					

IGT Systems	Feasibility Clinical Investigation Protocol AirWaze – easy and advanced tools for CBCT guided lung interventions	Doc ID: XCY607-130895 Rev: 04 Date: 2024-Jun-19 Page 42 of 56
-------------	--	--

Appendix II: CBCT-FS compared to CBCT

CBCT-FluoroSweep

- What is the purpose of the CBCT-FS scan?
 - Confirm tool-in-lesion
 - Determine location of the catheter compared to the lesion
 - Other,
- If confirm tool-in-lesion purpose, can you confirm tool-in-lesion based on the CBCT-FS scan?
 - Yes, there is tool-in-lesion confirmation.
 - No, there is no tool-in-lesion confirmation.
 - Inconclusive, because
- If confirm tool-in-lesion purpose AND tool-in-lesion confirmation, is the tool-in-lesion center-strike or off-center¹⁸?
 - Center-strike
 - Off-center strike
- To what extent is the CBCT-FS imaging useful to reposition or continue (for all purposes)?

Scan	1 Not useful at all	2	3	4	5 Very useful
CBCT-FS					

- Did you notice/experience any artefacts or glitches? If yes, please elaborate.
.....

CBCT (gold-standard imaging)

- What is the purpose of the CBCT scan?
 - Confirm tool-in-lesion
 - Determine location of the catheter compared to the lesion
 - Other,
- If confirm tool-in-lesion purpose, can you confirm tool-in-lesion (in all three orthogonal orientations) based on the CBCT scan?
 - Yes, there is tool-in-lesion confirmation in all three orthogonal orientations.
 - No, there is no tool-in-lesion confirmation.
 - Maybe, the quality of the CBCT scan is not sufficient to determine tool-in-lesion confirmation.
- If confirm tool-in-lesion purpose AND tool-in-lesion confirmation, is the tool-in-lesion center-strike or off-center¹⁸?
 - Center-strike
 - Off-center
 - Lesion is too small to define center-strike or off-center*
- Did the CBCT scan change your plan based on the CBCT-FS?
 - Yes
 - No
- Did you notice/experience any artefacts or glitches? If yes, please elaborate.
.....

* The lesion size is comparable to the catheter size.

IGT Systems	Feasibility Clinical Investigation Protocol	Doc ID: XCY607-130895
	AirWaze – easy and advanced tools for CBCT guided lung interventions	Rev: 04
		Date: 2024-Jun-19
		Page 43 of 56

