7.1. General

The AirWaze software tools for CBCT-guided diagnosis of peripheral pulmonary nodules will be studied at the Radboud University Medical Centre with the Principal Investigator described below:

Name Principal Investigator(s)	Name and address investigation site(s)
[name], MD, PhD Professor of Interventional Pulmonology	Radboud University Medical Center Nijmegen Department of Pulmonary Diseases [name], The Netherlands

An interview guide will be used to collect data regarding the primary endpoint. Data about the primary endpoints will be collected with semi-structured interviews as described in Appendix I: System Usability Scale (SUS) and Appendix II: CBCT-FS compared to CBCT.

A total of 37 prospectively included subjects in the Intention-To-Treat population are necessary to collect sufficient data for the evaluation of the objectives of this clinical investigation. After applying a drop-out rate of 10% of subjects will be lost, a total of 33 subjects in the Per Protocol population is required. More information on the statistical considerations can be found in Section 8.

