As performed routinely, an inspection bronchoscopy is performed at the start of the procedure. The selected pathway to the target lesion from the planning will be registered to and overlayed on the first performed CBCT. This overlay is visible at any time and will help the physician guide to the target lesion. If CBCT is indicated in conventional procedures, a low-dose CBCT-FluoroSweep scan will be performed of the same catheter and tool position. The CBCT-FluoroSweep has the same function as the regular CBCT, but it will be evaluated whether the low-dose CBCT-FluoroSweep is as accurate as the CBCT. Once tool-in-lesion is confirmed with either rEBUS, ROSE and/or CBCT-FluoroSweep (with regular CBCT as gold standard), tissue sampling is performed. If indicated, an EBUS is performed for staging lung cancer.

Follow-up

Safety follow-up visit will take place 1 week post-procedure (+7 days / -2 days). This visit may occur via phone or clinic visit. All adverse events that have occurred until this visit will be collected and monitored, including any prolonged hospital stay because of procedural complications, as well as unexpected complications.

[figure not shown]

Figure 3. Flowchart of the CBCT-guided navigation bronchoscopy procedure of the current clinical practice (bottom flow) and study practice with the AirWaze investigational device (top flow).

*Will be excluded from the PP population, see section 8.1.

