8.6. Primary objective

Objective

The primary objectives of this feasibility clinical investigation are to assess the overall system usability of the Philips AirWaze investigational device (version 1.1) as measured by the System Usability Score (SUS) and the accuracy of the tool-in-lesion confirmation scan CBCT-FluoroSweep compared to the conventional CBCT.

Primary Endpoints

The system usability will be assessed by using the System Usability Scale (SUS)¹⁵. An average SUS of greater than 70 will indicate a good usability design of the AirWaze Software solution. The SUS will be measured per operator every 4 procedures that they have operated the AirWaze software solution.

Image-based tool-in-lesion confirmation accuracy of CBCT-FS is defined as the number of procedures where CBCT-FS scans were adequate to define tool-in-lesion compared to conventional CBCT scans (gold-standard). The accuracy is defined as the sum of the number of tool-in-lesion in both CBCT-FS and CBCT, and the number of no tool-in-lesion confirmation in both CBCT-FS and CBCT, divided by the total number of CBCT-FS and CBCT pairs. Image based tool-in-lesion confirmation accuracy of 90% will indicate that the CBCT-FS is postulated to be sufficient for navigation bronchoscopy.

Analysis

The results will be analyzed by using the average SUS and the SUS score development in time. No statistical test will be performed on the SUS scores due to limited data points. A SUS greater than 70 will indicate a good usability design of the AirWaze software device. More information on the SUS questionnaire can be found in Appendix I: System Usability Scale (SUS).

The results will be analyzed by calculating the overall accuracy of the CBCT-FS for tool-in-lesion confirmation. More information on the CBCT-FS scan questions can be found in Appendix II: CBCT-FS compared to CBCT. An additional analysis will be performed within the tool-in-lesion confirmation group. Tool-in-lesion scans are evaluated and subdivided into center-strike and off-center confirmation scans¹⁸, subsequently the accuracy is calculated.

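### A purpose label given per scan, with no set time, decides which CBCT-FS/CBCT pairs get a tool-in-lesion reading, while section 8.6 divides by all pairs

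*Combined protocol and SAP*

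**What the plan says.** **How pairs arise.** Under section 7.4 (study practice), when a CBCT is indicated, "a low-dose CBCT-FluoroSweep scan will be performed of the same catheter and tool position". Appendix VI adds that the first scan of a procedure is a conventional CBCT, so pairs come from the additional scans.

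**How a pair is read.** Appendix II has one block per scan. The first block opens with "What is the purpose of the CBCT-FS scan" and the second with "What is the purpose of the CBCT scan". The answers offered are confirmation, catheter location relative to the lesion, or other. The reading depends on that answer in both blocks: "If confirm tool-in-lesion purpose, can you confirm tool-in-lesion based on the CBCT-FS scan" and "If confirm tool-in-lesion purpose, can you confirm tool-in-lesion (in all three orthogonal orientations) based on the CBCT scan". Appendix II gives no completion time and no rule for a pair whose two labels differ. Section 7.1 says "Data about the primary endpoints will be collected with semi-structured interviews as described in Appendix I" and names Appendix II in the same sentence, again without a time point for the label.

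**How accuracy is calculated.** Sections 7.1.1 and 8.6 add the pairs positive on both scans to the pairs negative on both, "divided by the total number of CBCT-FS and CBCT pairs". Purpose is not mentioned. The benchmark is: "Image based tool-in-lesion confirmation accuracy of 90% will indicate that the CBCT-FS is postulated to be sufficient for navigation bronchoscopy".

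**The concern.** The two scans of a pair are taken at one catheter and tool position because one CBCT was indicated. By design the pair has a single purpose, so a second label adds only the chance of disagreement.

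The label decides whether a yes/no reading exists, and it can be given after the image has been seen. Once the operator knows that the two scans disagree, or that one cannot be read, calling the scan a location check is a natural description in hindsight and needs no bad faith. Entry into a co-primary endpoint can then depend on its result.

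The form and section 8.6 also do not define the same set of pairs. The form scores confirmation pairs and the formula divides by all of them. An analyst will have to choose between the two after the data are in.

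**Working it through.** **The plan's own figure.** Section 8.2 gives 33 Per Protocol subjects and 10% drop-out: 33 / 0.9 = 36.7, rounded up to 37. This reproduces. The 33 rests on expert expectation, and no error rate or power is attached to the 90% benchmark.

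**Number of pairs.** Table 7 expects 1 to 3 CBCT-FS acquisitions per procedure. For 33 subjects that is 33 × 1 = 33 to 33 × 3 = 99 pairs. Only the per-procedure count is taken from Table 7; its study row carries a different sample size (n=22).

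**Effect of one label.** Assume 33 pairs, all labelled as confirmation, with 29 in agreement: 29/33 = 87.9%. Now one pair is labelled as location, or its two labels differ, so that it has no complete reading.

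| Pair that loses its reading | All pairs in denominator (8.6 as written) | Scored pairs only |
|---|---|---|
| Discordant or inconclusive | 29/33 = 87.9% (no change) | 29/32 = 90.6% (rises past 90%) |
| Concordant, positive or negative | 28/33 = 84.8% (falls) | 28/32 = 87.5% (falls) |

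Only the top right cell gives a gain.

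**The literal rule when labels are honest.** Let k of n pairs be true location scans or have mismatched labels. Even with perfect agreement elsewhere, accuracy cannot exceed (n − k)/n, so 90% needs k ≤ 0.1n. That allows 3 of 33 pairs (30/33 = 90.9%) or 9 of 99. With k = 4 of 33 the ceiling is 29/33 = 87.9%, and the benchmark is out of reach whatever the images show.

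**Scored-pairs rule: chance of meeting 90%.** Assume true accuracy p = 0.85, independent pairs, and up to m discordant pairs removed from the denominator. Sum C(n,x) p^x (1 − p)^(n−x) over all x with x / (n − min(m, n − x)) ≥ 0.9.

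| Pairs n | m = 0 | m = 1 | m = 2 |
|---|---|---|---|
| 33 | 25.0% | 43.6% | 62.6% |
| 66 | 11.6% | 20.8% | 32.6% |
| 99 | 6.0% | 10.6% | 17.4% |

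**Timing safeguards looked for.** Sections 7.1.1, 7.4, 8.6 and 9 and Appendix II contain no rule that the label precedes imaging, that the two labels agree, or that someone other than the operator checks them. Section 9 gives the e-CRF an audit trail, which records changes after entry but cannot show that a label came before the image. Appendix II is also not among the questionnaires that section 9 lets sites enter directly as source data. Section 5 puts the CBCT before the FluoroSweep, whereas the Appendix II question on whether the CBCT changed the plan implies that the CBCT-FS is judged first. Neither order places the label before imaging.

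**The case against.** The strongest reply is that section 8.6 already divides by all pairs. A reader might infer from the form that an operator can move a bad result out of the scored set and so lift accuracy over 90%. As written, the formula blocks that: a discordant pair relabelled as location stays in the denominator and still fails to count. This stands. The gain needs a restriction to scored pairs that the plan does not state. It does not settle the matter, because the literal formula counts every true location scan as a failure although no reading was requested. Pressure to restrict the denominator is therefore likely, and no rule is set in advance.

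A reader might also infer that negative readings in general are worth relabelling. They are not: a tool seen beside the lesion on both scans is a true negative and counts as agreement, so removing it cannot raise the figure.

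An unreadable scan does not have to be relabelled either. The form offers 'Inconclusive' for the CBCT-FS and 'Maybe' for the CBCT. But these options appear only after the confirmation label has been chosen, so they do not protect against a label chosen in hindsight.

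Further points on that side are fair. Purpose is the first item in each block, which suggests, without requiring, that it is answered first. The usefulness score, the question on a changed plan and the artefact questions do not depend on purpose, so a relabelled scan still leaves some trace. The summary includes usefulness for guidance in the primary endpoint, so location scans are intended data. Finally, this is a feasibility study with a benchmark and no test. These points limit the weight of the concern; none of them fixes the scored set.

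**Conclusion.** The concern holds in a limited form. A label given by the operator for each scan, at no fixed time, decides which pairs have a complete reading for a co-primary endpoint, and the stated denominator ignores that label. Under the literal formula, location-labelled and mismatched pairs pull accuracy down. Under a scored-pairs analysis, discordant or inconclusive pairs labelled as location in hindsight push it up.

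With 33 pairs, one label is enough to cross the benchmark: 87.9% becomes 90.6%. This assumes one pair per Per Protocol subject and 29 concordant pairs. With up to 99 pairs the effect of one label is smaller. The probabilities above also assume independent pairs and a true accuracy of 85%, which the documents do not give.

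The documents do not show that hindsight labelling will occur, and they do not support the reading that the plan as written lets an operator inflate the result. What they show is an opening that is cheap to close and a scored set that is not defined.

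**What to change.** 1. In Appendix II, replace the two purpose questions with one per pair, time-stamped before the first scan of the pair is acquired. This works whichever scan comes first.
2. Take the tool-in-lesion reading on both scans of every pair; at minimum, on every pair labelled as confirmation.
3. In sections 7.1.1 and 8.6, define the primary denominator as pairs whose pre-imaging purpose was tool-in-lesion confirmation. Keep inconclusive readings in the denominator as non-agreement.
4. Report a sensitivity analysis on all pairs, and list every pair whose purpose was changed later.
5. Enrolment began in October 2023 and this revision is dated June 2024, so some pairs may already exist without a pre-imaging label. Their label timing cannot be recovered; identify them and report them separately.

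The cost is a change to one form field, a time stamp, a few sentences in sections 7.1.1 and 8.6, and one short data entry per pair during the procedure. Reading every pair adds a question for location scans. No extra imaging is needed.
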